7.2.2 Analysis of the Primary Efficacy Endpoint(s)

Gait speed and Stride length

- Continuous variable (repeated measure)
- The Shapiro-Wilk test will be performed: histograms will be constructed, and measures of central tendency and dispersion will be calculated to test the assumption that distribution is normal
- If normality check will fail a transformation of the data will be done as corrective procedures (transformation will be made according to data distribution)
- Repeated-measures analysis of variance (RM-ANOVA) with tDCS (2 levels: Active and Sham) as the between-independent variable and Time (3 levels: Day 1, Day 10, and After 4-weeks) as the within-independent variable. In the inferential tests statistical significance will be set at 5% and all p-values is two-sided.

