3.3 Description of Study Design

This is an interventional, randomized, double-blind (participant and study staff), sham-controlled, parallel design, pilot study of N=80 RR-MS and SP-MS participants, characterized by mild to moderate gait dysfunctions. There will be a 1:1 random assignment of participants to receive either the active or the sham tDCS while performing the PA program. Blocked stratification will be used to randomize the participants to their respective study conditions. Block sizes of 4 and 6 will be used and the stratifying factor will be EDSS score (0-3.5 and 4.0-6.5). Randomization will be done by an independent randomizer who takes no part in baseline, follow-up, or sessions to maintain the double-blind nature of the study.

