3.4 Study Endpoints

3.4.1 Primary Study Endpoints

To determine the efficacy of the combination of tDCS and physical training, the following primary outcome measures have been chosen:

- Efficacy measured by comparison between the active and sham conditions by comparing the changes in gait velocity and stride length at baseline and participation end
- Compliance measured by 80% of participants having completed the study sessions

CONFIDENTIAL

This material is the property of the NYU School of Medicine and Langone Medical Center. Do not disclose or use except as authorized in writing by the study sponsor

Interventional Template Version: 28 APR 2017

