7.2.5 Baseline Descriptive Statistics

The demographic measurements and general characteristics (age, gender, height, BMI, EDSS scores) of the participants in the two groups will be compared at baseline using two-sample t-tests for continuous variables and the chi-square test for categorical variables. In the inferential tests statistical significance will be set at 5% and all p-values is two-sided.

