7.4 Measures to Minimize Bias

7.4.1 Enrollment/Randomization/Masking Procedures

Blocked stratification will be used to randomize the participants to their respective study conditions. Block sizes of 4 and 6 will be used and the stratifying factor will be EDSS score (0-3.5 and 4.0-6.5).

For the purposes of masking, the two conditions will be indistinguishable by the participant and administering study technician as all that separates the two conditions will be the sham tDCS. Sham tDCS is very effective in making participants believe they are receiving true treatment. A separate study technician or study PI will prepare the participant's condition so as to ensure the double blind.

CONFIDENTIAL

This material is the property of the NYU School of Medicine and Langone Medical Center. Do not disclose or use except as authorized in writing by the study sponsor

Interventional Template Version: 28 APR 2017

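### Randomisation is stratified by EDSS but no efficacy model contains the stratum, so tests are conservative to the extent that EDSS predicts the quantity tested

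*Combined protocol and SAP*

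**What the plan says.** **Design.** Section 3.3 states: "There will be a 1:1 random assignment of participants to receive either the active or the sham tDCS". Section 7.4.1 adds: "Block sizes of 4 and 6 will be used and the stratifying factor will be EDSS score (0-3.5 and 4.0-6.5".

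**Analysis.** Section 7.2.2 analyses gait speed and stride length by RM-ANOVA "with tDCS (2 levels: Active and Sham) as the between-independent variable". The same bullet sets "Time (3 levels: Day 1, Day 10, and After 4-weeks) as the within-independent variable". Section 7.2.1 gives this as the general approach, Section 7.2.3 repeats it for Timed Up and Go, sway and questionnaire scores, and the Protocol Summary names the same two factors. No stratum term, covariate or adjusted sensitivity analysis appears.

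**EDSS in the analysis text.** It appears only in Section 7.2.5, where "general characteristics (age, gender, height, BMI, EDSS scores) of the participants in the two groups will be compared at baseline".

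**Endpoint and test.** Section 3.4.1 defines primary efficacy by "comparing the changes in gait velocity and stride length at baseline and participation end". Section 7.2.2 sets the level: "In the inferential tests statistical significance will be set at 5% and all p-values is two-sided". The plan does not say whether the tDCS main effect or the tDCS-by-Time interaction decides.

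**The concern.** Blocking within strata makes the arms nearly equal in EDSS mix, so the stratum contributes almost nothing to the observed difference between arms. If the model omits the stratum, the variance that it explains stays in the error term all the same. The standard error then describes a less balanced design than the one used: intervals are too wide, the test is conservative and some power is lost. The sponsor chose EDSS as its only stratifying factor, which implies that it was thought prognostic. The plan takes on the stratification and then may not collect the benefit.

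How much is lost depends on which quantity is tested, and here the plan is not explicit. A main effect of tDCS compares average gait level. The tDCS-by-Time interaction compares change. EDSS could predict the first strongly and the second weakly or not at all.

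**Working it through.** **The plan's own figure.** There is none on this point. The nearest calculation, 19 per arm in Section 7.3, has no stratum in it. (A two-sided comparison of arms with those inputs gives 2 × (1.96 + 0.842)² × 0.23² / 0.196² = 21.6, so 22 per arm. That mismatch is a separate matter and does not bear on this one.)

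**Inputs from the documents.** 1:1 allocation in blocks of 4 and 6 within two strata (3.3, 7.4.1); two-sided 5% (7.2.2); baseline gait velocity 0.98 m/s, SD 0.23 m/s (7.3); 72 evaluable participants (4.5), about 36 per arm.

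**Assumptions.** Strata of equal size; stratum gap in gait speed 0.20-0.30 m/s; SD of change 0.15 m/s; stratum gap in mean change from 0 to 0.10 m/s.

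**Formulas.** For equal strata and near-exact balance:

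- stratum share R² = (gap/2)² / SD²
- SE ratio (reported to correct) = 1/√(1 − R²)
- true size = 2 × [1 − Φ(1.96 × SE ratio)]

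| Tested quantity | Gap (m/s) | SD (m/s) | R² | SE ratio | True size |
|---|---|---|---|---|---|
| Level (tDCS main effect) | 0.20 | 0.23 | 0.0100/0.0529 = 0.189 | 1.11 | 2.95% |
| Level (tDCS main effect) | 0.30 | 0.23 | 0.0225/0.0529 = 0.425 | 1.32 | 0.97% |
| Change (tDCS-by-Time) | 0 | 0.15 | 0 | 1.00 | 5.0% |
| Change (tDCS-by-Time) | 0.05 | 0.15 | 0.000625/0.0225 = 0.028 | 1.01 | 4.7% |
| Change (tDCS-by-Time) | 0.10 | 0.15 | 0.0025/0.0225 = 0.111 | 1.06 | 3.8% |

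For change, adjusting is worth 72/(1 − 0.028) = 74 to 72/(1 − 0.111) = 81 participants instead of 72, and nothing at a gap of zero.

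**Why the two contrasts differ.** Each participant's own level, including whatever EDSS adds to it, cancels when baseline is subtracted from a later visit. Only the part of EDSS that predicts change remains in the error for tDCS-by-Time. For the same reason, a stratum main effect alone leaves the tDCS-by-Time test unchanged; stratum-by-Time is the term that matters there.

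**Simulation of the planned three-visit model with no treatment effect.** N = 72, blocks of 4 and 6, two equal strata, correlation of 0.8 between visits before stratum-by-Time effects, stratum explaining 40% of stable between-subject variance in level (an assumption), 20,000 replicates; Monte Carlo SE about 0.15 points near 5%. Adjusted means with stratum and stratum-by-Time.

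| Share of change variance due to stratum | tDCS-by-Time, as planned | tDCS-by-Time, adjusted | tDCS main effect, as planned | tDCS main effect, adjusted |
|---|---|---|---|---|
| 0 | 5.14% | 5.14% | 1.46% | 5.06% |
| 5% | 4.59% | 5.05% | 0.99% | 4.91% |
| 10% | 3.68% | 4.68% | 0.72% | 4.90% |
| 20% | 3.16% | 4.91% | 0.50% | 4.97% |

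The 1.46% agrees with the formula. With a visit correlation of 0.8, 40% of stable variance is 0.8 × 0.40 / (0.8 + 0.2/3) = 0.369 of the variance of a three-visit mean, which gives an SE ratio of 1.26 and a size of about 1.4%.

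**The case against.** The strongest objection is that the primary endpoint is change. If EDSS does not predict change, the planned tDCS-by-Time test holds its 5% and the stratum adds nothing. The documents give no figure that links EDSS to change in gait, sway, Timed Up and Go or questionnaire scores. This stands, and it sets the lower end of the range at zero. A reader might infer from the omission that every 5% test in the plan runs below 5%, or that the 1% to 3% sizes apply to the primary endpoint. The documents support neither: those sizes belong to the main effect, under assumed gaps.

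The loss of power is also small at the planned effect. Take 0.196 m/s (20% of 0.98) as the arm difference in change, with 36 per arm. At an SD of 0.15 m/s, power exceeds 99.9% with or without the stratum. At an SD of 0.23 m/s and an 11% share it is 96.0% without and 97.0% with. At half the effect and an SD of 0.15 m/s, the gain is about 1 to 3 points. This stands too. So does the remark that unfinished blocks and the 10% dropout make balance within strata approximate rather than exact.

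Two things survive. First, the plan lists two factors and names no deciding contrast, so the main effect, where the loss could be marked, is not ruled out. Second, Section 7.3 frames improvement as a percentage of baseline. If change were proportional to baseline, strata 0.20-0.30 m/s apart would differ in mean change by 20% of that, 0.04-0.06 m/s. At an SD of change of 0.15 m/s, that is 2-4% of the variance and a size of about 4.8% to 4.5%: small, but not zero.

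**Conclusion.** The concern holds in a conditional form. The stratification factor is missing from every efficacy model, and the resulting tests run at or below 5%, to the extent that EDSS predicts the quantity tested.

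- **tDCS-by-Time (change, the primary endpoint):** from no loss to a modest one, with a true size from 5% to about 4.7-3.8% if the stratum explains 3-11% of the variance of change.
- **tDCS main effect (level):** possibly marked, about 3% to 1% for a stratum gap of 0.20-0.30 m/s.

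The gaps, the SD of change and the equal strata are assumptions, so no single corrected standard error can be stated. The direction is not in doubt: the error costs precision and power and does not create false positives. This is a free improvement rather than a threat to the trial's validity.

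**What to change.** In Sections 7.2.1 to 7.2.3:

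1. Add the EDSS stratum, coded as used at allocation (0-3.5 / 4.0-6.5), and stratum-by-Time to every RM-ANOVA. The stratum term serves the tDCS main effect; stratum-by-Time serves the tDCS-by-Time test.
2. Name the tDCS-by-Time contrast from baseline to treatment end as the deciding test for the primary endpoint.

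Cost: 1 degree of freedom for the stratum and 2 for stratum-by-Time with three visits, 3 in all. With 72 complete participants, the between-subject error goes from 72 − 2 = 70 to 69 degrees of freedom and the within-subject error from 2 × 70 = 140 to 2 × 69 = 138. It takes a sentence or two of text and no new data. Settling this before unblinding also removes a later choice between adjusted and unadjusted results.

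Replacing the RM-ANOVA by a model of the treatment-end value with baseline as covariate would be a different change. It should be decided on its own merits; none of the gains above was computed for it.

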Endpoint	Primary outcome measures: 
Comparison of change in gait velocity and stride length at baseline and participation end between the active and sham conditionsThe number of participants completing the study session (goal: 80% of the participants) Secondary outcome measures: 
% of remote tDCS sessions completedComparison between the active and sham conditions on functional mobility parameters (phase duration of Sit-to-Stand, Stand-to-Sit, Mid and End turning; acceleration and angular velocity) and the Timed Up and Go Task (TUG)Comparison between the active and sham conditions on EEG signals before and after the first and final tDCS sessionComparison between the active and sham conditions on static balance abilityComparisons between the active and sham conditions on Fatigue Severity Scale (FSS), 21-item Modified form of the Fatigue Impact Scale, 12-item Multiple Sclerosis Walking Scale, Multiple Sclerosis Quality of Life-54 (MSQOL-54)
Study Duration	Estimated study start date: June 2018 Estimated study end date:

CONFIDENTIAL

This material is the property of the NYU School of Medicine and Langone Medical Center. Do not disclose or use except as authorized in writing by the study sponsor
Interventional Template Version: 28 APR 2017

[figure not shown]
Participant Duration	Approximately 6 hours to 7 hours total over 9 remote sessions plus a baseline and a follow-up visit.
Duration of IP administration	20 minutes of tDCS in each daily session
Population	Age Eligible for study: 18 years to 70 years Sex Eligible for study: All Condition: Multiple Sclerosis
Study Sites	NYU Langone Health, USA
Number of participants	80 participants
Description of Study Agent/Procedure	
Device: Active tDCS tDCS is a therapeutic treatment that utilizes low amplitude direct currents (<4 mA) to induce changes in cortical excitability. Other Name: Soterix 1x1 tDCS mini-CTDevice: Sham tDCS During a sham session, the device is programmed to ramp up to the desired intensity (target 2.5 mA) and ramp down for the initial 60 seconds, with no current delivery during the session, and then again at the end of the session. These brief periods of stimulation serve to mimic the effects of a true stimulation session.Behavioral: Physical Activity (PA) program consisting of 20 minutes of cycling on an ergonomic cross-trainer.
Reference Therapy	N/A

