Key Procedures	20 minutes of tDCS combined with 20 minutes of PA
Statistical Analysis	Two way repeated-measures analysis of variance (ANOVA) with tDCS (active, sham) and Time (baseline, end treatment, 4 week follow-up)

CONFIDENTIAL

This material is the property of the NYU School of Medicine and Langone Medical Center. Do not disclose or use except as authorized in writing by the study sponsor
Interventional Template Version: 28 APR 2017

Schematic of Study Design

Flow diagram

CONFIDENTIAL

This material is the property of the NYU School of Medicine and Langone Medical Center. Do not disclose or use except as authorized in writing by the study sponsor

Interventional Template Version: 28 APR 2017

1 Key Roles

Principal Investigator

[name], Ph.D
Department of Neurology, NYU Langone Medical Center
[name]
[contact]

Co-Investigators

[name].
Director, Multiple Sclerosis Comprehensive Care Center
Department of Neurology, NYU Langone Medical Center
[name]
[contact]
[contact]

[name]
Department of Neurology, NYU Langone Medical Center
MS Comprehensive Care Clinic
[name]

2 Introduction, Background Information and Scientific Rationale

2.1 *Background Information and Relevant Literature*

Multiple Sclerosis (MS) is a frequent and common neurological disorder among young adults. Its course is characterized by a progressive neurological deterioration that can cause motor, sensory and cognitive dysfunction. Among the wide spectrum of signs and symptoms, tremor, spasticity, fatigue, and pain often present as well as balance and gait dysfunctions, which can be caused by a combination of fatigue, muscular weakness, and spasticity [Cameron and Wagner, 2011]. Gait alterations, which typically result in reduced speed, decreased step length and alteration of the physiological stance/swing phase duration [LaRocca et al., 2011; Pau et al., 2016; Pau et al., 2017] represent a serious issue for a large portion of people with MS (pwMS) (approximately 40% [LaRocca et al., 2011]) and negatively affects their quality of life. In fact, physical inactivity or sedentary lifestyle is common in patients with MS, and can initiate a cycle of deconditioning and worsening of symptoms [Motl et al. 2005; Motl et al., 2010]. By contrast, physical activity (PA) behavior, particularly exercise training, have beneficial effects on the various processes of MS [White et al., 2008].

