7.1 Statistical Hypotheses

Research hypothesis

There is a significant difference between active and sham groups by comparing primary and secondary outcomes at baseline and end treatment time.

Null hypothesis

There will not be a significant difference between active and sham groups

CONFIDENTIAL

This material is the property of the NYU School of Medicine and Langone Medical Center. Do not disclose or use except as authorized in writing by the study sponsor

Interventional Template Version: 28 APR 2017

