7.2 Description of Statistical Methods

7.2.1 General Approach

Study design of the study is a double- blind randomized controlled trial.

The primary, secondary outcomes and demographic variables will be examined with summary statistics, including means, medians, standard deviations (SD), minimum, and maximum values for continuous variables, and frequencies and proportions for categorical variables.

The characteristics of the participants in the two groups will be compared at baseline using two- sample t-tests for continuous variables and the chi-square test for categorical variables.

The Shapiro-Wilk test will be performed, histograms will be constructed, and measures of central tendency and dispersion will be calculated to test the assumption that distribution is normal. If the normality check will fail, a transformation of the data will be done as corrective procedures.

The general approach of statistical analyses will be a repeated-measures analysis of variance (RM-ANOVA) with tDCS (2 levels: Active and Sham) as the between-independent variable and Time (3 levels: Day 1, Day 10, and after 4-weeks) as the within-independent variable.

In the inferential tests statistical significance will be set at 5% and all p-values is two-sided.

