7.3 Sample Size

The sample size is calculated on the primary endpoint gait velocity measured before tDCS treatments at baseline time in a population of individuals affected by MS (0.98 ± 0.23 m/s). According to previous study the variability of changes after tDCS combined with PA is on average around 20% in active group compared with baseline assessment.

To recognize as significant change in gait velocity (alpha level = 0.05), equal to 20% difference between baseline and end of the treatment, a sample size of 19 cases for each arm will provide a power of 80%.

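### The primary RM-ANOVA has three time levels and no named deciding term, while the hypothesis concerns end of treatment; the primary time point is inconsistent and missing 4-week values are not addressed

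*Combined protocol and SAP*

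**What the plan says.** Section 7.2.2 gives one analysis for gait speed and stride length: an RM-ANOVA with group (active, sham) between participants and "Time (3 levels: Day 1, Day 10, and After 4-weeks) as the within-independent variable" within participants. Section 7.2.1 repeats it ("Time (3 levels: Day 1, Day 10, and after 4-weeks"), as does the Protocol Summary ("Time (baseline, end treatment, 4 week follow-up"). None of the three says whether the group main effect, the group-by-time interaction or a pairwise contrast decides, and none specifies a follow-up contrast.

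The question is stated differently in different places:

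- Section 7.1: "comparing primary and secondary outcomes at baseline and end treatment time".
- Section 7.3: "The sample size is calculated on the primary endpoint gait velocity", with a change "equal to 20% difference between baseline and end of the treatment".
- Section 3.4.1: "comparing the changes in gait velocity and stride length at baseline and participation end". The Protocol Summary has nearly the same words ("Comparison of change in gait velocity and stride length at baseline and participation end"). *Participation end* is not defined.
- Section 15: the primary efficacy row lists three times, the third at 4 weeks.

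The status of the 4-week visit also varies. The visit table in section 4.4 and the schedule in section 16 mark it Optional. Four places treat it as expected: inclusion criterion 8 in section 4.1, the prose of section 4.4, section 5.3.5, and the payment in section 12.2.

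Sections 8 and 9 cover blank CRF fields and data queries. No section says how missing values enter the analysis.

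**The concern.** The endpoint is worded as a change, which points to the group-by-time term. With three levels, that term asks whether the between-arm difference varies anywhere across baseline, treatment end and 4 weeks. It does not isolate treatment end, and a difference at 4 weeks alone can make it significant. With no deciding term named, a result could also be claimed from the main effect or from any pairwise comparison.

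The second problem is loss of participants. A conventional RM-ANOVA needs all three values from each person. Someone with valid baseline and treatment-end gait but no 4-week value would leave the primary test, although they supply everything the section 7.1 hypothesis needs. Section 4.5 allows 10% dropout but does not say whether a missed 4-week visit counts towards it.

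**Working it through.** **Inputs from the documents.** Baseline gait velocity 0.98 m/s, SD 0.23 m/s, 20% change, 19 per arm for 80% power (7.3). Two-sided 5% (7.2.2). 72 evaluable participants, 1:1, so 36 per arm (4.5, 3.3). 20% of 0.98 = 0.196 m/s. Day 1 and Day 10 are read as the baseline and end-treatment visits, as in the Protocol Summary.

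**Assumptions.** Section 7.3 describes 0.196 m/s as a change from baseline and gives no sham change, so using it as the between-arm difference d is an assumption. So are the within-person correlation ρ (equal between all visits), the share of the effect kept at 4 weeks, and 4-week attendance. An effect of 0.10 m/s is added as a smaller case.

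**The plan's own figure.** With 0.196 m/s as a between-arm difference, n = 2 × [0.23 × (1.960 + 0.842) / 0.196]² = 21.6, so 22 per arm. Power at 19 per arm is 74.7%. The stated 19 is not reproduced under the two-sided rule (a one-sided test gives 18). The planned 36 per arm exceeds all of these, so this does not decide the point.

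**Formulas** (noncentral F, n per arm, d_t the between-arm difference at each time):

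- Interaction: λ = (n/2) Σ(d_t − d̄)² / [SD²(1 − ρ)]; df 2 and 2(2n − 2).
- Treatment-end change contrast: same form with two times; df 1 and 2n − 2.
- Treatment-end ANCOVA on baseline: λ = (n/2) d² / [SD²(1 − ρ²)]; df 1 and 2n − 3. The EDSS stratum is not modelled.

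**Worked case: n = 36, d = 0.196, ρ = 0.5.** SD² = 0.0529.

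- Interaction, half kept, d_t = (0, 0.196, 0.098): Σ = 0.019208; λ = 18 × 0.019208 / 0.02645 = 13.07; power 90.3%.
- Change contrast: the same λ of 13.07 on 1 df; power 94.6%.
- ANCOVA: λ = 18 × 0.038416 / (0.0529 × 0.75) = 17.43; power 98.4%.
- Interaction, effect fully kept: λ = 17.43 on 2 df; power 96.7%.

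Power (%) with half the effect kept. The interaction columns are by 4-week attendance (n per arm); the last two columns use all 36 per arm.

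| d, ρ | 100% (36) | 90% (32) | 75% (27) | 50% (18) | Change | ANCOVA |
|---|---|---|---|---|---|---|
| 0.196, 0.5 | 90.3 | 86.4 | 79.5 | 60.3 | 94.6 | 98.4 |
| 0.196, 0.7 | 99.0 | 98.0 | 95.5 | 83.2 | 99.6 | 99.9 |
| 0.196, 0.8 | >99.9 | 99.9 | 99.5 | 95.2 | >99.9 | >99.9 |
| 0.10, 0.8 | 73.6 | 68.0 | 59.9 | 42.2 | 82.0 | 85.8 |

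Simulation (20,000 runs per setting) agreed with the interaction and ANCOVA columns to within about 1.2 points.

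**Does the choice of term matter?** For the group main effect, λ = (n/2) d̄² / [SD²(1 + 2ρ)/3], df 1 and 2n − 2. At 0.196 m/s and 36 per arm, over ρ 0.5 to 0.8, power is 83 to 72% if the effect is fully kept at 4 weeks and 31 to 25% if it is lost. The term chosen therefore matters a good deal.

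**Does the interaction isolate treatment end?** As a logical check only, set d_t = (0, 0, 0.098), a pattern that no section predicts. At ρ = 0.5, λ = 18 × 0.0064027 / 0.02645 = 4.36. The interaction rejects in 44 / 66 / 84% of trials at ρ 0.5 / 0.7 / 0.8, while treatment-end ANCOVA rejects at its nominal 5%.

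**The case against.** Several points on the other side stand.

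- A reader might infer that the plan plainly tests the wrong question. The documents do not support that. If the section 15 table governs, three time points match the primary measurement times. The supported fault is an inconsistent primary time point with no deciding term named. Sections 7.1 and 7.3 favour treatment end, but making it primary is a choice that the plan still has to state.
- A reader might infer that the three-level model always costs power. It does not. At 0.196 m/s and ρ 0.5, with full attendance and the effect fully kept, the interaction (97%) is no worse than the change contrast (95%). Part of ANCOVA's advantage is baseline adjustment, not re-targeting.
- A reader might infer that many participants will skip the 4-week visit. Criterion 8, the section 4.4 prose, section 5.3.5 and the $50 payment, half the total, treat it as expected. No section supports 50% attendance; that column only marks the far end of a range.
- Deletion of incomplete cases is not written in the plan. It follows from conventional RM-ANOVA; section 7.2.2 names no software or complete-case rule.
- The 44 to 84% rejections are not false positives. They detect a real difference at 4 weeks, but they do not show one at treatment end.
- Sham participants also exercise, so the between-arm effect may be below 0.196 m/s. This qualifies every 0.196 figure above.

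The study is a pilot, which limits the weight of the point. It still states an efficacy hypothesis tested at two-sided 5%, so the deciding comparison should be named.

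**Conclusion.** The concern holds in this form. The plan's single primary efficacy analysis names no deciding term, its documents disagree on the primary time point, and it has no rule for participants who lack a 4-week value. A significant interaction would not by itself answer the section 7.1 hypothesis.

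The power cost is conditional. At an assumed 0.196 m/s with half the effect kept, going from full to 90% attendance costs about 4 points at ρ 0.5, 1 point at ρ 0.7 and under 1 point at ρ 0.8. The cost is material if attendance is low or the effect is smaller: at 0.10 m/s and ρ 0.8, 74% at full attendance falls to 60% at 75% attendance, against 82% for the change contrast. A claim that the trial is underpowered because of this model would go beyond the documents. The point should be fixed, mainly for interpretability and to avoid needless loss of data.

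**What to change.** Name the between-arm difference in gait velocity at treatment end as the primary test. Use ANCOVA adjusted for baseline velocity and the EDSS randomisation stratum (0-3.5, 4.0-6.5), in all randomised participants with a treatment-end value. A mixed model on all available visits, with the same contrast named as primary, is an alternative under different missing-data assumptions. Naming that contrast within the planned RM-ANOVA would settle the target, but if incomplete cases are dropped it would not recover them.

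Analyse stride length the same way and state its place relative to velocity. Make the 4-week contrast secondary. State how missing treatment-end and 4-week values are handled.

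Define *participation end*, which sections 6.4.4 and 7.4.3 also use. Reconcile sections 3.4.1, 7.1 and 15 on the primary time point, and sections 4.1, 4.4, 5.3.5, 12.2 and 16 on whether the 4-week visit is optional.

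The cost is an amendment that needs IRB approval before it is implemented (section 10.2), and the 4-week visit leaves the primary test. No new data, visits or participants are needed: baseline and treatment-end velocity and the EDSS stratum are already collected.

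### The primary gait analysis enters baseline as a level of Time, not as a covariate; this is unbiased but gives up precision that a change of wording would recover

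*Combined protocol and SAP*

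**What the plan says.** Section 3.4.1 defines the efficacy endpoint as an active-versus-sham comparison made "by comparing the changes in gait velocity and stride length at baseline and participation end". Section 7.2.2 gives the model: "Repeated-measures analysis of variance (RM-ANOVA) with tDCS (2 levels: Active and Sham) as the between-independent variable", with "Time (3 levels: Day 1, Day 10, and After 4-weeks) as the within-independent variable". The Protocol Summary lists the same three levels as "Time (baseline, end treatment, 4 week follow-up", so Day 1 is the pre-treatment measurement. Section 7.2.3 repeats the model for the Timed Up and Go, sway and questionnaire outcomes.

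No section names a baseline covariate, an analysis of covariance, a model that constrains the baseline means to be equal, or an EDSS term. Sections 3.3 and 7.4.1 stratify randomisation by EDSS (0-3.5 and 4.0-6.5). In Section 7.2.5 the characteristics "of the participants in the two groups will be compared at baseline using two-sample t-tests for continuous variables"; the variables listed there are age, gender, height, BMI and EDSS, not gait, and no adjustment follows from the tests. The plan does not say which term of the model, tDCS or tDCS by Time, decides the primary comparison.

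**The concern.** Baseline gait is measured before treatment, so it carries no information about the treatment effect except through its correlation with later gait. A model uses that information best when baseline is a covariate. With baseline as an outcome level, the baseline-to-end contrast subtracts the whole baseline value, although later gait regresses only part of the way on it. The contrast is then noisier than it need be, and in a given sample it over-corrects for a chance baseline difference. The tDCS main effect, if it were read as the test, averages in a value that treatment cannot have changed.

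At stake is the precision of the active-versus-sham estimate for both primary gait variables and, through Section 7.2.3, for many secondary scores.

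**Working it through.** **Inputs.** Baseline gait velocity 0.98 m/s with SD s = 0.23 m/s, and a target change of 20%, so 0.20 × 0.98 = 0.196 m/s (Section 7.3). 72 evaluable participants (Section 4.5), so 36 per arm under 1:1 allocation. Two-sided 5% (Section 7.2.2). Assumed, because the documents do not give them: r from 0.5 to 0.9; equal SDs and equal correlations across visits; all 72 measured at all three visits; an illustrative arm difference of 0.10 m/s.

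**The plan's own figure.** Section 7.3 states 19 per arm for 80% power. Read as a two-arm comparison of 0.196 m/s with SD 0.23, n = 2 × [(1.960 + 0.842) × 0.23/0.196]² = 21.6, so 22 per arm (23 with the t distribution). Power at 19 is 75% (72% with t). The stated 19 does not reproduce at two-sided 5%, but nothing below depends on it.

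**Precision of the baseline-to-end contrast.**
- Change score: SE = s × √[2(1−r) × 2/36].
- Baseline as covariate: SE = s × √[(1−r²) × 2/36].
- Variance ratio, adjusted to change: (1−r²)/[2(1−r)] = (1+r)/2. The saving is (1−r)/2.
- Equivalent number of participants: 72/[(1+r)/2].

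At r = 0.7 the change SE is 0.23 × √(0.6 × 0.0556) = 0.0420, and the adjusted SE is 0.23 × √(0.51 × 0.0556) = 0.0387.

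**Power of the planned interaction.** The noncentrality is (36/2) × Σ(dⱼ − d̄)²/[s²(1−r)] on 2 and 140 degrees of freedom, where dⱼ is the arm difference at visit j.
- Effect fully kept at 4 weeks, d = (0, 0.10, 0.10), r = 0.7: 18 × 0.00667/0.01587 = 7.56, power 0.68. Fully lost, d = (0, 0.10, 0), gives the same value.
- Half kept, d = (0, 0.10, 0.05): 18 × 0.005/0.01587 = 5.67, power 0.55.

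| r | SE change | SE adjusted | Variance saved | Participants equivalent to 72 | Power 0.10: change | Power 0.10: adjusted | Power 0.10: interaction, kept or lost | Power 0.10: interaction, half kept | Power 0.196: change | Power 0.196: adjusted |
|---|---|---|---|---|---|---|---|---|---|---|
| 0.5 | 0.0542 | 0.0469 | 25% | 96 | 0.44 | 0.56 | 0.455 | 0.35 | 0.946 | 0.984 |
| 0.7 | 0.0420 | 0.0387 | 15% | 85 | 0.65 | 0.72 | 0.68 | 0.55 | 0.996 | 0.999 |
| 0.8 | 0.0343 | 0.0325 | 10% | 80 | 0.82 | 0.86 | 0.856 | 0.74 | 1.00 | 1.00 |
| 0.9 | 0.0242 | 0.0236 | 5% | 76 | 0.98 | 0.99 | 0.992 | 0.96 | 1.00 | 1.00 |

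Powers for the two contrasts use the noncentral t; those for the interaction use the noncentral F. A simulation of the three-level model with 0.098 m/s at both later visits agrees: interaction 0.664 against adjusted 0.694 at r = 0.7, and 0.838 against 0.841 at r = 0.8.

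**Chance imbalance.** Ignoring stratification, the SE of the baseline difference is 0.23 × √(2/36) = 0.054 m/s. Given a one-SE difference, the change estimate moves by (1−r) × 0.054 in the opposite direction: 0.027, 0.016, 0.011 and 0.005 m/s at the four values of r. At r = 0.7 that is 0.016/0.042, about 39% of the estimate's own SE.

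**Main effect, if used.** An effect of 0.10 m/s at both later visits is diluted to (0 + 0.10 + 0.10)/3 = 0.067 m/s. At r = 0.7 its SE is 0.23 × √[(1+2r)/3 × 2/36] = 0.0485, and power is about 27%. The share of a baseline difference carried into this average is (1+2r)/3, or 80% at r = 0.7.

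**The case against.** The planned analysis is valid. Under 1:1 randomisation the change contrast is unbiased and keeps its 5% error rate. A reader might infer that leaving baseline out as a covariate biases the result. It does not: the imbalance shift exists only conditional on the baseline difference that happens to occur.

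On the plan's own effect, little is lost. For 0.196 m/s at 36 per arm, both contrasts have about 95% power or more from r = 0.5 upward. This stands. However, Section 7.3 describes the 20% as a change in the active group from its own baseline, and both arms exercise, so the active-versus-sham difference could be smaller. Precision matters there.

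The rise from 65% to 72% is measured against a single change contrast. A reader might take it as the gain over the planned test, but the planned interaction pools error over three visits. If the effect is fully kept or fully lost at 4 weeks, it is about four points behind at r = 0.7, level near 0.8 and slightly ahead at 0.9. This also stands, with two limits. The interaction is an omnibus test that does not isolate the comparison in Section 3.4.1, and it falls further behind if the effect partly persists (0.55 against 0.72 at r = 0.7).

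A reader might also infer that the baseline t-tests are the plan's only answer to imbalance. They are not, because randomisation is stratified by EDSS. Two broad bands limit imbalance in gait speed only partly, though, and the stratum is absent from the model. Nor is a baseline difference carried whole into the main effect; the share is (1+2r)/3.

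**Conclusion.** The point holds as a matter of efficiency, and I would label it a free improvement. For the contrast that Section 3.4.1 names, the planned form has 2/(1+r) times the variance of a baseline-adjusted model. Adjustment saves 25% of the variance at r = 0.5 and falls to 5% at r = 0.9. The power gain over the planned interaction depends on r and on how far the effect persists at 4 weeks, and the documents give neither. It ranges from material (r = 0.7 or below, or partial persistence) to nil (r near 0.8 or above, effect fully kept or lost).

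The direction of the variance result is certain for any r below 1. The power figures rest on the assumed r, equal correlations, complete visits and an illustrative 0.10 m/s. The gain from adding the EDSS stratum is not quantified. The documents do not support a stronger claim that the primary analysis is invalid, biased or underpowered for its stated effect on this account.

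**What to change.** In Section 7.2.2, make the primary comparison the active-versus-sham difference in treatment-end gait velocity, and likewise stride length, from a linear model with arm, the participant's own baseline value and EDSS stratum. Report the adjusted difference with its 95% confidence interval. Model the 4-week value in the same way, or fit one mixed model to both post-treatment visits with baseline as a covariate. Use the same form for the continuous secondary scores in Section 7.2.3.

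This also states which comparison decides, and it frees the primary result from the 4-week visit, which the Schedule of Events marks as optional.

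The cost is a change of analysis wording, made before outcomes are examined by arm. Baseline i-10MW is already scheduled for every participant (Section 5.3.2 and the Schedule of Events), and EDSS is needed for randomisation in any case. No new data, visits or participants are required.
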